3.4. Endpoints/Outcomes Measurements

3.4.1.Primary outcomes.

Primary outcomes will include the differences between the intervention and control groups' pre-/postintervention levels of pain (Numeric Rating Scale) and anxiety (Numeric Rating scale) (Appendix K).

Theoretical Concept and Measurement	#	Score	Reliability
	Items	Range	
Demographics			
As delineated in Data Retrieval Form	12		
Pain (Primary outcome)			
Visual Analog Scale: Measures pain intensity. Higher scores indicate higher levels of pain	1	0-10	* r =0.96 literate patients r= illiterate
Anxiety (Primary outcome)			
Hospital Anxiety Scale: Measures intensity of anxiety. Higher scores indicate higher levels of anxiety	16	0-14	Cronbach's alpha 0.73**
Healing Touch			-

* (Hawker, Mian, Kendzerska, & French, (2011). * Ferraz., Quaresma, Aquino, Atra, Tugwell, P., & Goldsmith, 1990).

**Al Aseri, Suriya, Hassan, Hasan, Sheikh, Al Tamimi, Alshathri M, Khalid N. (2015).

3.4.2.Secondary outcomes

Secondary outcomes include the relationship between HT and demographic information of the subjects. As well, the feasibility of introducing HT as a therapy for postpartum women will be assessed.

3.5. Consent/Assent

All participants in the HT intervention group and control group will provide informed consent. Acquiring consent is a twostep process: (1) Participant returning and electronic consent via the survey platform, and then (2) the site PI/SUB-I has a conversation with the participant over the phone or face to face to review the consent. Once screened for eligibility, a member of the research team may call the potential participant using the consent phone call script (Appendix H). Whether over the phone or face to face, the study personnel will describe the study, answer any questions they may have, and if the participant is interested, email them an electronic consent form and the HIPPA authorization form if they haven't already received one. Both of these forms will be managed through an electronic platform, and securely load into the platform to be accessed by

the PI and study personnel. Participants who complete the electronic consent form will be included in the study, and randomized into either the intervention or control group. Informed consent will be confirmed again with the women prior to starting the study intervention or control session, since they may have changed their mind after delivery. One copy of the consent and HIPAA forms will be given to the participant (via email or face to face), and one will be kept in the research file for the participant, as well as being scanned into the electronic medical record.

3.6. Monitoring Subjects and Criteria for Withdrawal of Subjects from the Study.

Study participants may voluntarily withdraw from the study at any time. During the Healing Touch Therapy, the intervention would stop and a subject would be withdrawn if: The woman or her family at the bedside requested the intervention stopped, the woman reported an increase in pain and needs assistance, the woman had a self-identified change in clinical status and requested medical assistance, the woman needs to stop the session to care for the baby or get out of bed / leave the room for some reason.

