3.2. Control Group

This study has a control group. For the control group: a member of the research team, who may or not be a HT practitioner, will verify consent. Then they will ask the woman to complete baseline measurements of pain and anxiety. The subject will then be encouraged to have a quiet time session equivalent to the length of a Healing Touch session, with the lights dimmed. After the quite time, the team member will again measure the subject's levels of pain and anxiety.

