4.2. Method of Data Analysis

Exploratory and descriptive analysis will be completed for all study variables. Variables will be examined for normality and examined with means and standard deviations or medians and interguartile ranges accordingly. Statistical analyses will be conducted using a data management and analysis platform. Summary descriptive statistics will be analyzed for the main outcome variables. To examine the research question, an independent sample t-test will be conducted to assess if differences exist on pain and anxiety by Intervention or Control Group. An independent samples t-test is the appropriate statistical test when the purpose of research is to assess if differences exist on a continuous (interval/ratio) dependent variable by a dichotomous (2 groups) independent variable. The assumptions of normality and homogeneity of variance will be assessed. Normality assumes that the scores are normally distributed (bell-shaped) and will be assessed using the one-sample Shapiro-Wilk test (Razali & Wah, 2011). Homogeneity of variance assumes that both groups have equal variances and will be assessed using Levene's test for equality of variances (Levene, 1960). If the Levene's test for equal variance indicates that equal variances cannot be assumed ($p \le .05$), a Welch's t-test will be used instead of the Student's t-test, which is more reliable when the two samples have unequal variances (Ruxton, 2006). The t-test will be two-tailed with the probability of rejecting the null hypothesis when it is true set at p < 0.05. This ensures a 95% certainty that the differences did not occur by chance.

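### Section 3.6 withdraws Healing Touch women who report more pain and need assistance, with no quiet-time counterpart and no stated analysis; if their scores are lost, the pain comparison leans modestly towards Healing Touch

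*Combined protocol and SAP*

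**What the plan says.** The combined protocol and SAP deals with withdrawal in section 3.6. The general provision covers both arms: "Study participants may voluntarily withdraw from the study at any time". The specific provision is worded for one arm: "During the Healing Touch Therapy, the intervention would stop and a subject would be withdrawn if" one of a list of events happens. The list includes "the woman reported an increase in pain and needs assistance". It also includes a request to stop by the woman or her family, a change in clinical status that she identifies herself, and practical reasons such as "the woman needs to stop the session to care for the baby".

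For the control arm, section 3.2 says "The subject will then be encouraged to have a quiet time session" of the same length, and then "After the quite time, the team member will again measure" pain and anxiety. It lists no events that end the session or withdraw the woman.

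Section 3.1 says that pain and anxiety are measured again after Healing Touch and that the session is documented. It does not say whether this holds when a session is cut short.

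Section 3.4.1 makes the between-group difference in pre- and post-session pain and anxiety the primary outcome. In section 4.2 the analysis is that "an independent sample t-test will be conducted to assess if differences exist on pain and anxiety by Intervention or Control Group", with Welch's version if variances differ. No analysis population, missing-data method or treatment of withdrawn women is given.

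**The concern.** One withdrawal trigger is a primary outcome moving the wrong way, and it is written for the tested arm only. In its ordinary sense, a woman withdrawn from a study contributes no further data. If site staff read section 3.6 that way, some of the Healing Touch women whose pain rose would have no post-session score, while a quiet-time woman with the same experience would be measured as usual. The Healing Touch mean would then look better than it is even if the therapy did nothing.

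The oversampling from 128 to 160 (sections 2.4 and 4.1) replaces numbers. It does not replace scores that are lost selectively. Four sites could also read the same wording differently.

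Ending a session for any of the listed reasons is not questioned here. The gap is what happens to the data afterwards.

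**Working it through.** **1. The plan's own figure.** Inputs from section 4.1: two-sided alpha 0.05, power 0.80, d = 0.5, equal allocation. The normal approximation is n per arm = 2(1.960 + 0.842)²/0.5² = 62.8, so 63. The noncentral t calculation gives 63.77, so 64 per arm and 128 in total, with power 0.801. The stated 128 reproduces. Recruiting 160 leaves room for 1 − 128/160 = 20% loss, but no expected dropout or withdrawal rate is stated.

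**2. Assumptions, because the plan gives no rate.** There are 160/2 = 80 women per arm, no true effect and normal scores. Scores of k Healing Touch women are lost and none in control. The correlation ρ between the withdrawal trigger and the analysed score is 1, 0.7, 0.5 or 0.32. A value of 1 is an upper bound, since the trigger also requires that the woman needs assistance. The triggers unrelated to pain weaken the link further.

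**3. Bias.** With a fraction w = k/80 lost from the upper tail, the shift in the Healing Touch mean is −ρ·φ(z)/(1 − w) SD, where z is the 1 − w normal quantile.

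- k = 4: w = 0.05, z = 1.645, φ(z) = 0.103, and 0.103/0.95 = 0.109. Times ρ: 0.109, 0.076, 0.054, 0.035 SD. Against d = 0.5 this is 0.035/0.5 = 7% to 0.109/0.5 = 22%.
- k = 8: w = 0.10, z = 1.282, φ(z) = 0.1755, and 0.1755/0.90 = 0.195. Times ρ: 0.195, 0.137, 0.098, 0.062 SD.

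**4. Type I error.** Simulated Student's t-test, 40,000 null trials per setting (Monte Carlo SE about 0.0011), deleting the k Healing Touch women with the highest trigger values:

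| Lost (of 80) | ρ = 1 | ρ = 0.7 | ρ = 0.5 | ρ = 0.32 |
|---|---|---|---|---|
| 1 | 0.057 | 0.053 | 0.051 | 0.050 |
| 2 | 0.070 | 0.059 | 0.054 | 0.052 |
| 4 | 0.115 | 0.079 | 0.064 | 0.055 |
| 8 | 0.255 | 0.142 | 0.096 | 0.067 |

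The excess favours Healing Touch. With 4 lost, false positives in that direction are 0.110, 0.071, 0.053 and 0.041 against a nominal 0.025. If each woman instead leaves when her own trigger passes a fixed threshold, an expected 4 losses give 0.108, 0.077, 0.063 and 0.054, so the one-arm result hardly depends on this choice. Under a milder mechanism, 4 lost at random among women more than 0.5 SD above the mean give 0.070, and among all women above the mean 0.059.

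**5. Change or post-session score.** Section 4.2 does not say which is tested. The trigger is an increase in pain, and for equal pre and post variances the correlation of change with the post score is √((1 − r)/2), where r is the pre–post correlation. This is 0.50 at r = 0.5 and 0.32 at r = 0.8, so the effect is weaker on the post score. A check with rounded 0–10 scores (assumed mean 4, SD 2; 4 lost; trigger correlated 1 or 0.7 with the increase) gives:

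- change tested: 0.117 or 0.081 at r = 0.5, and 0.108 or 0.079 at r = 0.8;
- post score tested: 0.069 or 0.060 at r = 0.5, and 0.057 or 0.054 at r = 0.8.

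**6. Loss in both arms.** With individual thresholds, equal expected loss (4 v 4) gives a bias of about zero and a type I error of 0.050, 0.051, 0.049 and 0.052 at the four correlations. If control loses half as many (4 v 2), it is about 0.063, 0.055, 0.053 and 0.052.

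**The case against.** The strongest reply is that the harm rests on a premise the plan never states. Section 3.1 promises reassessment without qualification, and sections 4.3.1 and 5.4 send the session data to the site coordinator for entry. Nothing says a stopped woman's data are discarded. A reader might infer that the plan excludes these women from the analysis. The documents do not support that: score loss is an inference from the section heading and the word withdrawn. This part of the reply stands. What remains is that section 3.6 states a one-arm rule and no section says what it means for the scores.

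Second, quiet-time women also have babies to feed and may also be in pain, and they may leave voluntarily. That stands too, and it would offset part of the bias. A reader might still expect matched loss to inflate the type I error. A simulation that always deletes exactly the four highest values in each arm does show up to 0.071, but this is an artefact of fixing the number deleted. When withdrawal depends on each woman's own symptoms, the rate is nominal.

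Third, the trigger must occur within a single session of about 15 minutes (section 2.3) described as no more than minimal risk (section 5.1), so it may be rare. That is plausible, and it limits the size of the problem without closing the gap.

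Last, a reader might infer that safety information is lost. Section 7 has the principal investigator review each woman's data and the session notes, so the point concerns the efficacy comparison only.

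**Conclusion.** The point holds in a limited form. The asymmetry in wording and the silence on analysis are in the text. The bias towards Healing Touch on pain is conditional on the scores being lost, and lost in that arm more than in the other.

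On the stated assumptions, 1 or 2 losses out of 80 are of little consequence. Four would give a modest distortion, larger if change is tested than if the post-session score is tested, and at the top of the range only if the trigger tracks the analysed score almost perfectly. Eight would raise the type I error to about 0.07 to 0.25, but no section suggests that number.

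It would be tempting to say that the trial's pain result is materially biased. That has not been shown, because neither the frequency of such withdrawals nor the fate of the scores is documented. Severity is minor to moderate. The case for acting is that the exclusion is tied to a primary outcome, that scores not taken at the time cannot be recovered, and that the remedy is cheap.

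**What to change.** Leave the conditions for ending a session to the sponsor, and reconcile sections 3.2, 3.6 and 4.2 with one data rule for both arms, for example:

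*If a Healing Touch or quiet-time session ends early for any reason, post-session pain and anxiety scores are recorded at that point where the woman agrees, with the time and the reason. She is analysed in her randomised arm unless she withdraws consent for the use of her data.*

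Section 3.6 should then say whether withdrawn refers to the session or to the study. Report early endings by arm and reason. For women with no post-session score, add to section 4.2 one sensitivity analysis that is unfavourable to Healing Touch, with values chosen by the sponsor in advance.

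The cost is protocol wording, a place to record the time and reason (the Appendix K form was not available for review), and one extra analysis. No additional staff should be needed. The downsides are that a few scores will be taken before 15 minutes, some women will decline to give one, and the estimate may be less favourable to Healing Touch. If sites already score stopped sessions, the change only writes that practice down.

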4. STATISTICAL CONSIDERATIONS/DATA ANALYSIS

4.1. Sample Size

Power analysis for an independent sample t-test was conducted in G-POWER to determine a sufficient sample size using an alpha of 0.05, a power of 0.80, a medium effect size (d = 0.5), and two tails. There will be an equal allocation of participants into each group. Based on the aforementioned assumptions, the desired sample size is 128 (64 in each group). The team will over sample in order to meet sufficient sample size. Planned recruitment will = 160 women (40 per study site).

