1.3. Background and Significance

During the past two decades, cesarean delivery rates have increased dramatically worldwide. Currently in the United States, nearly one third of all newborns are born by cesarean.¹ Inova Health System performed over 7 000 cesarean deliveries in 2019 (IAH 1201; IFOH 950; IFMC 4,031; ILH 872). "Women who experience cesarean births are at risk for anesthetic, surgical, and postoperative complications. They have longer hospitalizations and recoveries after childbirth compared with women who experience vaginal births".² Pain and anxiety are the most common complications after cesarean delivery. Pain is ranked highest among undesirable clinical outcomes associated with post-operative cesarean deliveries. Conventional methods of managing pain following cesarean delivery include intrathecal morphine and post-operative oral narcotic pain medications. The use of these opioids is accompanied by side effects including nausea, vomiting, pruritus, sedation, dizziness, bladder dysfunction, reduced gastrointestinal motility, and sleep pattern disturbance.³

The traditional practice of administering opioids for pain control may impair the women's abilities to remain awake and alert during the critical transition to parenting, to provide effective care for and feeding of their newborns, develop positive maternal-infant bonds, and return to optimal health. Non-pharmacological strategies for the management of postoperative pain and anxiety play an important role in routine clinical practice after cesarean delivery. Effective relief of pain and anxiety can cause comfort, enhanced quality of life, faster return to everyday life, shorter hospital stays and lower hospitalization costs. The importance of alternative pain and anxiety management strategies and decreased opioid administration cannot be overstated for this population.

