3. STUDY METHODS AND PROCEDURES

3.1. Study Treatment/Intervention

If the woman completes the consent form, they will be enrolled in the study and randomized into either the intervention or control group. When they are admitted to the postpartum unit after cesarean delivery, based on their randomization, the study coordinator at each site will schedule either 1) a Healing Touch (HT) practitioner for the intervention group OR 2) a non-HT practitioner who will collect data for the control group. The HT practitioners for this study will be registered nurses or HT practitioners who work in the Inova Health System and have received the minimum of Foundations of Healing Touch training. All study personnel entering patient care areas will abide by universal precautions, plus masks and face shields as required by the hospital system for infection control. For the intervention group, the HT practitioner will verify consent. Then they will ask the woman to complete baseline measurements of pain and anxiety. The practitioner will then administer the HT intervention consisting of a full body, pain management technique focusing on the surgical site, and wound sealing. HT techniques (Field Repatterning, Pain Syphon, Beak Fingers Lasering,) are techniques specific to management of pain and clearing of the energy field that have been used frequently by the nurses in their delivery of patient care. The HT intervention to be used in the proposed study has been developed by co-investigator, [name], Certified Healing Touch Practitioner and Instructor, to focus on the symptom management needs of the study participants (post-cesarean delivery) and should take no more than 15 minutes to complete. Levels of pain and anxiety will be reassessed post-intervention. Nurses providing the HT intervention will document the session and other outcomes as described below. There is a risk that the patient will not receive Healing Touch if: there is not a HT provider available or the patient is discharged prior to availability of the HT provider.

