10. FACILITIES AND EQUIPMENT

All four hospital facilities have the same resources and equipment available to the study team. All study personnel have access to password protected computers in the facilities. Across the four facilities the postpartum rooms are all private, and allow for consistency of the intervention.

11. OUTSIDE CONSULTANTS/COLLABORATORS None

None

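### The four-site pooled t-test has no site term; if loss falls mainly on the Healing Touch arm and varies by site, the estimate may be biased in either direction, and adjustment is cheap

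*Combined protocol and SAP*

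**What the plan says.** Sections 2.4 and 4.1 set the same quota at each of four hospitals: "Planned recruitment will = 160 women (40 per study site"). The sample size is derived "using an alpha of 0.05, a power of 0.80, a medium effect size (d = 0.5), and two tails", with the statement that "There will be an equal allocation of participants into each group", and arrives at this: "the desired sample size is 128 (64 in each group"). Section 3.3 allocates by an online coin toss; it describes neither blocking nor stratification by site.

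Section 4.2 plans a Student t-test, or a Welch test if variances differ, whose purpose is to "assess if differences exist on a continuous (interval/ratio) dependent variable by a dichotomous (2 groups) independent variable". Arm is the only factor. On combining sites, section 4.3.1 says only that the principal investigator will synthesise the data.

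Three places bear on loss:
- Section 3.1 says a woman may not receive HT if "there is not a HT provider available or the patient is discharged prior to availability of the HT provider". Sessions are scheduled by each site's coordinator.
- Sections 3.1 and 3.2 let someone who is not an HT practitioner run the control session.
- Section 4.3.1 says that a shortage of HT providers can prevent scheduling of either kind of session.

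No loss rate, provider count per site, outcome level per site or analysis set is given.

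**The concern.** The HT arm needs a trained practitioner at the bedside before discharge; the control arm does not. If cover is better at some hospitals than at others, the analysed HT arm may lean towards the well-covered hospitals while the control arm keeps its equal site mix. Any difference between hospitals in the analysed score would then pass into the pooled mean difference. It could create an apparent effect or hide a real one. Comparing women within hospitals removes that component, and hospital is known for every woman.

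**Working it through.** **The plan's own figure.** With d = 0.5, two-sided alpha 0.05 and equal arms, the exact noncentral t gives power 0.795 at 63 per arm and 0.801 at 64 per arm. So 64 per arm (128 in total) reproduces. The step from 128 to 160 implies an allowance of 1 − 128/160 = 20%, although no dropout rate is stated.

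**Bias from site mix.** Inputs from the documents: four sites of 40 women and 1:1 allocation, so 20 women per arm per site in expectation. Assumptions, because the documents give no values: two sites lose a fraction L of their HT women, the other two lose none, controls lose none, and the two pairs of sites differ by S (in SD) in the analysed score.

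- Share of the analysed HT arm from the high-loss sites: w = (1 − L)/(2 − L). The control share is 1/2.
- Size of the bias: (1/2 − w) × S. Its sign depends on which pair of sites scores higher.

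| L | w | 1/2 − w | S = 0.3 | S = 0.5 | S = 1.0 |
|---|---|---|---|---|---|
| 25% | 0.429 | 0.071 | 0.02 | 0.04 | 0.07 |
| 50% | 0.333 | 0.167 | 0.05 | 0.08 | 0.17 |

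For S of 0.3 to 0.5 the range is 0.021 to 0.083 SD. Dividing by 0.5 gives 4% to 17% of the design effect. At L = 50% the women lost number 2 × 20 × 0.5 = 20 of 160 (12.5%), which is inside the implied 20% allowance.

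**Effect on the test.** Simulation of 4 × 40 women with coin-toss allocation, within-site SD of 1 and 10,000 runs per scenario. The first four rows assume no true HT effect.

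| Loss pattern | S | Pooled bias (SD) | Pooled type I error |
|---|---|---|---|
| None, or 20% of HT women at every site | 0.25 to 1.0 | about 0 | 0.048 to 0.052 |
| 0% vs 40% by site, both arms alike | 0.25 to 1.0 | about 0 | 0.050 to 0.055 |
| 0% vs 40% by site, HT only | 0.5 | 0.06 | 0.064 |
| 0% vs 40% by site, HT only | 1.0 | 0.125 | 0.102 |

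With a true effect of 0.5, the HT-only 0% vs 40% pattern and the site difference running against HT, pooled power is 0.70 at S = 0.5 and 0.51 at S = 1.0. The model with arm and site has power of about 0.82 in both cases. Across the scenarios with no HT effect, its bias is at most 0.003 SD and its type I error is 0.047 to 0.054.

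**Precision without differential loss.** With 4 × 32 = 128 women, the total SD fixed and d = 0.5, power with and without the site term is 83% vs 81% if sites explain 10% of the variance, about equal at 5%, and about 1 point lower with the term if sites do not differ. With 160 women and the within-site SD fixed, the figures are about 0.87 vs 0.86 at S = 0.5, and 0.87 vs 0.80 at the extreme S = 1.0.

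**The case against.** The strongest objection is that the documents do not establish the mechanism. Section 4.3.1 extends provider shortage to quiet-time sessions, and if loss is equal in the two arms the bias is about zero even when it varies by site. That stands, and it rules out any claim that the HT arm will drift. It does not settle the matter. Section 4.3.1 concerns women who cannot be scheduled after consent, and it does not make clear whether they have already been allocated. Section 3.1 separately foresees discharge before an HT provider is free, and describes no matching loss for controls.

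Variation of loss by site is also an inference. The coordinators are local, but the practitioners are described only as working in the health system, and section 1.3 counts HT-trained nurses system-wide.

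Nor do the documents say which score enters the test. Section 3.4.1 speaks of levels before and after the session. If change scores are analysed, only site differences in change matter, and differences in pain or anxiety level cancel.

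A reader might infer more from three facts, and none supports it:
- The caesarean volumes ("IAH 1201; IFOH 950; IFMC 4,031; ILH 872") differ by 4,031/872 = 4.6-fold. This shows difference in size, not in outcome, and the equal quotas fix the planned site mix whatever the volume.
- A coin toss will often split a site unevenly. With 32 analysed women the chance of 20:12 or worse is 0.215 per site, and 1 − (1 − 0.215)⁴ = 0.62 for at least one of four. That is chance imbalance, which the test's error rate already covers; it is not bias.
- Pooling four hospitals does not itself turn site differences into an apparent HT effect, because allocation gives both arms the same expected site mix.

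In the other direction, section 10 says "All four hospital facilities have the same resources and equipment available to the study team" and that postpartum rooms are private. It does not address HT cover, patients or outcome levels, so it does not remove the risk.

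**Conclusion.** The point holds conditionally. The plan leaves site out of both allocation and analysis. Bias arises only if three things coincide: loss mainly in the HT arm, loss that varies by site, and sites that differ in the score analysed. The documents make the first plausible but ambiguous and are silent on the other two. Under the moderate assumptions above the bias is about 0.02 to 0.08 SD against a design effect of 0.5 SD, and it can favour or mask HT. It becomes serious only at extreme values, such as a 1 SD site difference. Without such loss, omitting site costs a little precision at moderate site differences and nothing in validity. This is a cheap improvement, not a defect that undermines the trial.

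**What to change.** In section 4.2, make the primary comparison for each outcome a linear model with arm and a four-level fixed site effect, so that the reported difference is the within-site difference. Tabulate randomised, lost and analysed women by arm and site, which will show whether differential loss occurred. Keep the pooled t-test as a sensitivity analysis.

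The cost is a line of text, one table and 3 degrees of freedom: about 1 point of power if the sites are identical. No new data and no larger sample are needed. The site term removes bias from site mix only. It does not correct selective loss within a site, so the table should be read with that limit in mind.
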